5.3.10. Clinical remission, clinical response, and corticosteroid-free clinical remission

The following remission and response will be assessed at M12, M24, M36 and M48:

Clinical remission is achieved when all the following criteria are met in the components of the Mayo Score:

- rectal bleeding sub-score = 0
- central endoscopy sub-score <= 1
- stool frequency sub-score <= 1.

Clinical response is defined as:

- reduction in Total Mayo Score of at least 2 points and >= 30 percent from baseline
- with an accompanying decrease in rectal bleeding sub-score of >= 1 point or absolute rectal bleeding sub-score of <= 1 point.

Corticosteroid-free clinical remission is defined as clinical remission at M12, M24, M36 and M48, and concomitant corticosteroid free for ≥ 12 weeks prior to these timepoints among patients with clinical remission after 8 weeks of induction treatment (at baseline of ABX464-102 study).

5.3.11. Endoscopic improvement and endoscopic remission

Endoscopic improvement is achieved if the Mayo central endoscopic sub-score is 0 or 1.

Endoscopic remission is defined as Mayo central endoscopic sub-score = 0.

5.3.12. Hematology and biochemistry

For hematology and biochemistry local laboratory will be used. All lab dosages will be done locally.

Any hematology and biochemistry safety sample (Total bilirubin, AST/ALT, Alkaline phosphatase, Lipase INR, Prothrombin, high-sensitivity (hs) Troponin I & T, CPK and NT-proBNP) that does not have a result reported at any visit must be repeated (e.g. if sample is hemolyzed). The sample should be repeated as soon as possible (and recorded as an unscheduled visit in the eCRF).

Each laboratory value that is outside of the institution's normal range will be identified. The investigator will be responsible for assessing the clinical significance of laboratory abnormalities. If the investigator is uncertain about the clinical significance of a laboratory abnormality, he/she will consult with the Sponsor medical monitor. The investigator should follow any clinically significant laboratory abnormalities until resolution.

Table displays the clinical laboratory parameters that must be measured.

Table 2: Laboratory Tests

HEMATOLOGY	BIOCHEMISTRY	STOOLS
Hemoglobin	Sodium	Faecal calprotectin
Hematocrit	Potassium	
WBC	Chloride	
Neutrophils	Calcium	
Lymphocytes	Phosphate	
Monocytes	Glucose	
Eosinophils	BUN or urea	
Basophils	Creatinine	
Platelet count	AST	
ESR	ALT	
Fibrinogen	GLDH	
Prothrombin time and/or INR	Lipase	
	Alkaline phosphatase	
	gGT	
	Total bilirubin	
	Total protein	
	Albumin	
	LDH	
	CRP	
	CPK	
	High-sensitive Troponin T and/or I	
	NT-proBNP	
	Amylase	

The indicative volumes drawn per study visit are presented in the following table.

	COLLECTION TUBE
Hematology (Hemoglobin, Hematocrit, Red Cell Count, MCV, MCHC, Platelets, White cell count with diff.)	2mL EDTA tube
Fibrinogen and Prothrombin Time and/or INR	4,5 mL Na-citrate tube
NT-proBNP	2mL K2 EDTA tube
Biochemistry panel incl CRP, Serum Pregn. and hs Troponin (I and/or T)	3.5mL serum gel tube
miR-124 determination at M12, M36, M48 only	5mL of total blood (PAXgene tube)
ESR	5mL ESR tube

6. INVESTIGATIONAL PRODUCT(S)

All investigational products to be used in this study have been manufactured, packaged and labelled by contract manufacturers for ABIVAX, according to GMP standards and are supplied to investigators free of charge.

6.1. Description of investigational treatment

The study treatment that will be administrated to subjects enrolled in this follow-up study consists of capsules containing ABX464 given orally once daily.

6.2. Description of investigational Product

6.2.1. Active investigational product (ABX464)

The ABX464 investigational medicinal product (IMP) is a hard gelatin capsule intended for oral administration.

For the proposed clinical trial, the IMP consists of size 01 capsules containing 50 mg of ABX464 drug substance in the form of granulate prepared with a number of common excipients (microcrystalline cellulose, polyvinylpyrrolidone, magnesium stearate and colloidal silica). It is supplied in high-density polyethylene bottles closed with high-density screw caps.

ABX464 will be manufactured by:

DELPHARM Lille SAS
[name]
[name]
[name]
[name] France

Primary packaging labelling as well as Qualified Person release of the IMP are performed at the following site:

CREAPHARM CLINICAL SUPPLIES (previously SODIA)
[name]
[name]

The study drug should not be stored above 30°C (86°F) and should not be frozen or refrigerated.

6.3. Administration and Dosing

6.3.1. Administration of the investigational product

Subjects will be dosed with a daily dose of 50 mg that is 1 capsule every day.

Subjects will be orally dosed in fed condition (regular breakfast) with a cup of water.

A subject diary, in which the subject should report the number of capsules taken and the intake time, will be given to the subject at baseline. Moreover, this diary will enable the subject to report also potential discomfort or side effects s/he could experience.

The last study treatment intake should be the day before M48 visit.

6.3.2. Guidelines for treatment postponement and dose modifications

No intra-subject dose escalation/dose adjustment are allowed.

6.4. Method of Assigning Subjects to Treatment Arms

All subjects will be assigned a unique and incremental subject Identification (ID) number (i.e. the same than the one used in the ABX464-101 study). Subject IDs will be unique (i.e. reallocation of the ID will not be permitted). The format will be a seven-digit number as follows: ABX-country/site number (4 digits) – subject number (3

digits). The latter 3-digit subject number will be assigned according to the subject's order of inclusion in the center.

Study treatment dispensation will be performed at each study visit. In all cases, subject should return his/her used and unused bottles at each study visit for a compliance check.

6.5. Packaging

The IMP consists in hard gelatin, powder-filled capsules (size 01) containing 50 mg of ABX464, supplied in high-density polyethylene bottles closed with high-density screw caps.

6.6. Storage

ABX464 will be shipped to the investigational site at ambient temperature. The study drug should not be stored above 30°C (86°F) and should not be frozen or refrigerated.

The IMP should not be used beyond the expiration date. Drug supplies are to be stored in a secure, limited-access location under the storage conditions required by GCP/GMP guidelines.

6.7. Product Accountability

An accurate and current accounting of the dispensing and return of IMP(s) will be maintained on an ongoing basis by the pharmacist and a member of the study site staff in the Accountability Log and case report form and will be verified by the study's monitor.

6.8. Prior and Concomitant Medication

6.8.1. Allowed concomitant treatment

Mandatory and/or allowed Concomitant Medications are:

- ABX464 once daily at 50 mg.
- Oral 5-aminosalicylic acid at stable dose.
- Immunosuppressants in the form of azathioprine, 6-mercaptopurine, or methotrexate at stable dose.
- Antidiarrheals (e.g., loperamide, diphenoxylate with atropine) at stable dose.
- COVID-19 vaccines are allowed.

Potential other concomitant medications should be kept at constant dose during the course of the study and properly reported in the medical file of the subject and the eCRF.

This information should include the name of the medication (international nonproprietary name), daily dosage, duration and indication.

6.8.2. Prohibited concurrent medications

The following drugs are prohibited during the course of the study.

- Anti-tumor necrosis factor (TNF) therapies.
- Vedolizumab.
- JAK inhibitors.
- Topical corticosteroids and topical 5-aminosalicylic acid preparations.
- Cyclosporine and tacrolimus.
- Drugs that could interact with ABX464 should be avoided especially the CYP1A2 inducers/inhibitors. The following CYP1A2 inducers/inhibitors are prohibited during the whole course of the study (ciprofloxacin,

enoxacin, fluvoxamine, montelukast, phenytoin, rifampicin, ritonavir, teriflunomide). Please refer to Appendix #1.

The UGT1A9 inhibitors and OAT P1B1/P1B3 inhibitors/substrates that could interact with ABX464 and its metabolite ABX464-N-Glu should also be avoided. Please refer to Appendix #1.

- Use of any investigational or non-registered product within 3 months preceding Day 0 except ABX464.

7. SUBJECT COMPLETION AND WITHDRAWAL

7.1. Subject Completion

Treatment duration with ABX464 is 48 months or earlier if one study discontinuation criterion is met (defined below).

The subjects exiting the study must perform the Follow-up and End of Study (EoS) visits 4 weeks after last study drug intake. They will be then treated according to the standard of care upon study treatment interruption.

7.2. Study discontinuation criteria

Subjects who are not found eligible or not willing to enter the ABX464-108 study are not considered as prematurely discontinued as they have completed the scheduled treatment of ABX464-102 study.

A subject can be withdrawn at any time from the study for the following reasons:

Subject's study discontinuation could occur for the following reasons:

- Investigator's decision;
- An Adverse Event or an intercurrent condition that preclude continuation of treatment;
 - specifically, an increase $\geq 3.0 \times$ ULN in liver transaminases (AST/SGOT and/or ALT/SGPT) or an increase $\geq 2.0 \times$ ULN in Alkaline phosphatase or in total bilirubin requires close observation with repeating liver enzymes and serum bilirubin tests two times weekly and clinical investigation to understand the etiology of this elevation. Frequency of retesting can decrease to once a month if abnormality stabilizes after the initial two weeks of follow-up and if the patient is asymptomatic. Discontinuation of the study treatment should occur if:
 - ALT or AST $> 8 \times$ ULN
 - ALT or AST $> 5 \times$ ULN for more than 2 weeks
 - ALT or AST $> 3 \times$ ULN and total bilirubin $> 2 \times$ ULN or INR > 1.5
 - ALT or AST $> 3 \times$ ULN with appearance of fatigue, nausea, vomiting, right upper quadrant pain or tenderness, fever, rash, and/or eosinophilia ($> 5\%$);
 - Severe (grade 3 or higher) infection, a severe (grade 3 or higher) opportunistic infection, or sepsis;
 - Any cardiac AESI or condition diagnosed during the course of the study and assessed by the clinical adjudication committee as changing the risk/benefit balance for the subject;
 - New onset of acute pancreatitis;
 - Malignancies (including non-melanoma skin cancers);
 - Any relevant toxicity or negative change in the risk/benefit assessment leading to an unacceptable risk for the subject or any data deriving from other clinical trials or toxicological studies which negatively influence the risk/benefit assessment. This may be applicable but is not limited to the following cases: occurrence of AEs which character, severity or frequency is new in comparison to the existing risk profile, or clinically significant abnormal laboratory results, including new onset anemia (defined as a hemoglobin decrease > 2 g/dL from baseline or hemoglobin < 8 g/dL
 - Worsening of the UC defined as a 2-point increase in the pMMS, with pMMS ≥ 4 on 2 separate occasions 7 day-apart and confirmed by an endoscopy sub score of 2 points or higher; subject who would experience a treatment failure during the study may be withdrawn at any time. S/he will have to be treated according to standard of care as soon as s/he is discontinued from study treatment because of study withdrawal;
 - Withdrawal of consent;
 - Pregnancy;
 - Patients included with a history of cardiac ischemic disease and/or congestive heart failure will be discontinued from the study, will perform the End of Study Visit 4 weeks after last study drug administration and will then be treated according to the standard of care upon study treatment interruption.
 - Administrative reasons from Sponsor.

7.3. Study Discontinuation

All subjects, regardless of the completion or premature discontinuation, should perform the Follow-up and End of Study Visits according to the study flow-chart.

8. ADVERSE EVENTS (AE), ADVERSE EVENT OF SPECIAL INTEREST (AESI) AND SERIOUS ADVERSE EVENTS (SAE)

The investigator is responsible for the detection and documentation of events meeting the criteria and definition of an AE, AESI or serious adverse event (SAE). During the study, in case of a safety evaluation, the investigator or site staff will be responsible for reporting AEs, AESIs and SAEs, as detailed in this section of the protocol.

During the screening period, only adverse event related to the screening procedures will be collected.

Any disease progression will not be reported in the eCRF as an adverse event, but will be documented in the efficacy section.

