2.3. Primary Endpoint

The primary endpoint of this study is defined as the number of incidences of treatment-emergent adverse events in the ABX464 treated subjects.

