8.1. Definition of an AE

Any untoward medical occurrence in a subject or clinical investigation subject administered a pharmaceutical product and which does not necessarily have to have a causal relationship with this treatment.

An AE can therefore be any unfavorable and unintended sign (including an abnormal laboratory finding), symptom, or disease (new or exacerbated) temporally associated with the use of a medicinal product, whether or not considered related to the medicinal product.

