8.3. Definition of a SAE

A serious adverse event (experience) or reaction is any untoward medical occurrence that, at any dose:

- a) Results in death

NOTE: Death is an outcome of an AE, and not an AE in itself. Event which led to death should be recorded with fatal outcome.

- b) Is life-threatening

NOTE: The term 'life-threatening' in the definition of 'serious' refers to an event in which the subject was at risk of death at the time of the event. It does not refer to an event, which hypothetically might have caused death, if it were more severe.

- c) Requires hospitalization or prolongation of existing hospitalization

NOTE: In general, hospitalization means that the subject has been detained (usually involving at least an overnight stay) at the hospital or emergency ward for observation and/or treatment that would not have been appropriate in the physician's office or out-patient setting. Complications that occur during hospitalization are AEs. If a complication prolongs hospitalization or fulfills any other serious criteria, the event is serious. When in doubt as to whether "hospitalization" occurred, or was necessary, the AE should be considered serious.

Hospitalization for elective treatment of a pre-existing condition that did not worsen after informed consent was given is not considered an AE.

- d) Results in persistent or significant disability/incapacity,

NOTE: The term disability means a substantial disruption of a person's ability to conduct normal life functions. This definition is not intended to include experiences of relatively minor medical significance such as uncomplicated headache, nausea, vomiting, diarrhea, influenza, and accidental trauma (e.g. sprained ankle) which may interfere or prevent everyday life functions but do not constitute a substantial disruption.

- e) Is a congenital anomaly/birth defect

- f) Is another medically important condition: This refers to an AE that may not be immediately life-threatening or results in death or hospitalization but may jeopardize the subject or may require intervention to prevent one of the outcomes listed above. Based on medical and scientific judgment this should usually be considered serious.

If there is any doubt about whether or not an AE is serious, the investigator should contact the sponsor.

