8.3.1. Events and/or Outcomes Not Qualifying as SAEs

Any hospitalization, or prolongation of hospitalization due to the circumstances listed below, will not be reported as SAE:

- planned medical/surgical procedure;
- planned medical/surgical admission (planned prior to entry into study, appropriate documentation required), for the disease under study;
- Administrative or social reasons (e.g. lack of housing, economic inadequacy, care-giver respite, family circumstances).

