8.4. Events or Outcomes Qualifying as AEs or SAEs

8.4.1. Clinical laboratory parameters

Abnormal laboratory findings (e.g., clinical chemistry, hematology) or other abnormal assessments (e.g. vital signs) that are judged by the investigator as **clinically significant** will be recorded as AEs or SAEs if they meet the definitions of sections 8.1 and 8.2 respectively. Clinically significant abnormal laboratory findings or other abnormal assessments that are detected during the study or are present at informed consent and significantly worsen during the study will be reported as AEs or SAEs. Clinically significant abnormal laboratory findings or other abnormal assessments that are associated with the disease being studied, and are present at the start of the study but do not worsen, will **not** be reported as AEs or SAEs. However, if these findings or assessments are judged by the investigator to be more severe than expected considering the subject's condition, then they may be reported as AEs or SAEs.

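### Protocol Section 8 keeps all disease progression out of the eCRF adverse event data, against 8.1, 8.3, 8.3.1 and 8.5, so an unplanned admission for a UC flare can be missing from the TEAE and serious TEAE counts

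*Protocol*

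**What the plan says.** The introductory text of protocol Section 8, just before 8.1, contains this rule: "Any disease progression will not be reported in the eCRF as an adverse event, but will be documented in the efficacy section". Neither document defines disease progression for UC, and the rule makes no exception for serious or drug-related events.

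The rest of Section 8 reads differently:

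- **8.1** counts as an adverse event any "symptom, or disease (new or exacerbated) temporally associated with the use of a medicinal product, whether or not considered related to the medicinal product".
- **8.3** begins "A serious adverse event (experience) or reaction is any untoward medical occurrence that, at any dose" and lists among the criteria "Requires hospitalization or prolongation of existing hospitalization".
- **8.3.1** lists the hospitalisations that are not SAEs: those for a planned procedure, a "planned medical/surgical admission (planned prior to entry into study, appropriate documentation required), for the disease under study", and those for administrative or social reasons. An unplanned admission for UC is not on the list.
- **8.5** requires every AE, AESI and SAE from consent until four weeks after treatment ends to be entered in the eCRF. SAEs and AESIs must also go to the safety vendor within 24 hours.

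The primary endpoint in protocol 2.3 is the "number of incidences of treatment-emergent adverse events in the ABX464 treated subjects". Protocol 2.4 adds the number of serious TEAEs as a secondary endpoint. SAP 9.1 says outputs are programmed from CRF data. SAP 11.6.1 refers to protocol Section 8 for further adverse event definitions and procedures.

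**The concern.** The primary objective is long-term safety, and the primary endpoint is a count of what sites enter as adverse events. A rule that removes a class of events before entry therefore acts directly on the endpoint. In this population the class is not remote: protocol 1.1.2 says that acute severe UC needs hospital care.

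For one and the same event, the protocol gives a site two instructions that cannot both be followed. Sites may resolve the conflict differently, so the count would depend partly on which passage each site read. Any omission lowers the reported number of events.

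The rule also acts too early. Protocol 8.6 asks the investigator to weigh the course of the underlying disease when judging the causality of a recorded event. If the event is set aside as progression, that question is never asked in the adverse event record.

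**Working it through.** The plan states no figure to reproduce on this point: there is no sample-size calculation and no expected event rate. The check is a reading of the passages against one test case, followed by arithmetic for scale.

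**1. Test case: an unplanned hospital admission for a UC flare during treatment.**

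| Protocol text | What it tells the site |
|---|---|
| Section 8, opening | If the flare is disease progression: no AE entry in the eCRF; efficacy section only |
| 8.1 | An exacerbated disease is an AE, related or not |
| 8.3 | Hospitalisation makes it an SAE |
| 8.3.1 | No exemption applies, because the admission was not planned |
| 8.5 | The SAE must be in the eCRF |

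The first row conflicts with the other four taken together. Reading a flare as progression is an inference, but a reasonable one, since the rule sends the event to the efficacy section. The one softening clause, in 8.4.1, says that "if these findings or assessments are judged by the investigator to be more severe than expected considering the subject's condition, then they may be reported". It covers laboratory findings and other abnormal assessments only, and it permits rather than requires.

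**2. From the eCRF to the tables.** The SAP shells give Listing 16.2.7, the adverse event listing, as the source of the TEAE and serious TEAE tables. An event not entered as an AE cannot reach them, and nothing in the SAP brings UC worsening back in.

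**3. Does the efficacy side replace the lost data?** Only in part. SAP 11.3.1.2 counts worsening when there is a 2-point rise in Total Mayo Score, three days of bleeding and endoscopic confirmation. Listing 16.2.6.2 then shows only times. Withdrawal for UC worsening has a row in Table 14.1.2, medications are recorded with their indication (protocol 6.8.1), and procedures appear in Listing 16.2.10. None of these carries seriousness, grade, causality or outcome for the flare.

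**4. Expedited reporting.** The Section 8 rule names only the eCRF. The 24-hour report in 8.5 and 8.7 uses a separate form. A site could report the flare on that form and still leave it out of the eCRF, or do neither. The DSMB's 7-day review (protocol 3.1.2) covers only SAEs that are potentially causally related.

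**5. Scale.** Protocol 1.3 gives 22 enrolled patients, 15 previously on ABX464 and 7 previously on placebo.

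- Each omitted flare lowers the TEAE count and the serious TEAE count by one event.
- An omitted patient with no other SAE lowers the share of patients with an SAE by 1/22 = 4.5 points in the total column, and by 1/15 = 6.7 or 1/7 = 14.3 points in that patient's group column.
- Exact 95% intervals (Clopper-Pearson): 0/22 gives 0 to 15.4%; 1/22 = 4.5% gives 0.1 to 22.8%; 2/22 = 9.1% gives 1.1 to 29.2%.
- The frequency of hospitalised flares is not in the documents. If a proportion p of patients has one during the study, the chance of at least one among 22 is 1 − (1 − p)^22. For assumed p = 2%, 5%, 10% and 15% this is 36%, 68%, 90% and 97%.

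**The case against.** The strongest defence is that the Section 8 sentence is a deliberate carve-out from a general definition. It sends flares to the efficacy endpoints and avoids counting them twice, and the study is single-arm and descriptive with no hypothesis test. For non-serious flares that stands as a legitimate choice. For a flare that meets an 8.3 criterion it does not, because 8.3.1 sets out the SAE exemptions and leaves this case off the list.

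A second defence is timing. Protocol 5.3.1 says that all ongoing patients had already passed Month 36, so a changed sentence cannot govern most of the data. That stands, and it is why the remedy needs a retrospective query.

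Several stronger readings are tempting but go beyond the documents:

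- *Expedited reporting is barred.* It is not: the SAE form is a separate route, and 8.3 tells sites to treat doubtful hospitalisations as serious.
- *Only Mayo scores would be recorded.* Withdrawal reason, medications and procedures are captured too.
- *Any colectomy admission is covered by the contradiction.* 8.3.1 exempts planned procedures without a time limit, so a planned colectomy could be exempt.
- *Flares are the commonest serious event, or some particular number of patients had one.* The documents give no such breakdown or count.
- *The patient who withdrew at Month 1 is a missed flare.* Protocol 1.3 says lack of efficacy and mentions no flare or admission.
- *Drug-caused diarrhoea or abdominal pain is being lost as progression.* Protocol 1.2.5 names both as anticipated adverse events, so sites are told to expect them; misclassification is possible but not shown.

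**Conclusion.** The contradiction is real and concerns which events enter the primary endpoint. An unplanned hospital admission for a UC flare can be absent from the TEAE and serious TEAE counts, depending on which protocol passage a site followed. Where it has an effect, the effect is to undercount. Loss of expedited reporting is possible but conditional.

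The 4.5 points per omitted patient is an upper limit. It assumes that the patient had no other SAE and that the site left the flare out of the eCRF adverse event data. The total effect cannot be given, because the documents do not say how many such admissions occurred or how sites handled them. The conclusion also assumes that sites take disease progression to include a UC flare.

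**What to change.** 1. **Protocol Section 8.** Reconcile the opening rule with 8.1, 8.3, 8.3.1 and 8.5. Define disease progression for UC and limit the exemption to UC activity that is neither serious nor judged related to ABX464. UC worsening that meets an 8.3 criterion and is not exempt under 8.3.1, or that is judged related, is recorded as an AE or SAE with grade, causality and outcome.
2. **Before lock.** Query each site once for past UC hospitalisations and surgery, and enter qualifying events. SAP 1.1 says treatment was still ongoing at the time of writing, and SAP 9.5 places a data review meeting before lock, so there is a natural point to settle this.
3. **SAP 11.6.1.** State how UC worsening is counted, and show the TEAE table (14.3.1.5) and the serious TEAE table with and without UC preferred terms. The latter is numbered 14.3.1.8 in SAP 11.6.1 but 14.3.1.7 in SAP 14.1 and the shells, so cite it by title.

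UC worsening whose only consequence is discontinuation can stay in the disposition table, where it already has a row.

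The cost is a short protocol clarification, one query covering at most 22 patients, and a few repeat tables. The reported TEAE and SAE counts may rise slightly.
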